5.2 Study Visits

5.2.1 Screening Period

The Screening period (Days -30 to -1) consists of two study visits:

- Screening Visit 1
- Screening Visit 2.

The time to Screening Visit 2 can be extended to more than 30 days to obtain an appropriately and fully completed bladder diary or to obtain a valid bladder diary (see Section 17.6). In addition, where a UTI occurs after completion of the bladder diary and impacts the ability to perform urodynamics the time to Screening Visit 2 can be extended until the UTI is resolved.

5.2.1.1 Screening Visit 1

The suggested order of procedures for Screening Visit 1 is shown in [Table 6](#).

Table 6 Order of Procedures for Screening Visit 1

Suggested order of procedures	Comment	Details of procedure
1. Informed consent	Must be performed before all other study procedures	Section 5.2.2.1
2. Demographic data		Section 5.2.2.2
3. Medical/surgical/NDO history		Section 5.2.2.2
4. Prior medications and therapies		Section 5.2.2.2 Section 6.4
5. Concomitant medications and therapies		Section 5.2.2.2 Section 6.4
6. Prior and concomitant treatments for NDO		Section 5.2.2.2
7. Inclusion/exclusion criteria		Section 4.1 Section 4.2
8. Adverse events	To be monitored and collected from the time the subject signs the informed consent form	Section 8.1
9. Vital signs	Must be performed prior to any invasive procedure at the visit. Body weight and height to be measured as part of vital signs at Screening Visit 1.	Section 8.4
10. Physical examination (symptom based)	Clinically significant abnormalities should be reported as medical history.	Section 8.3
11. Urine pregnancy test	To assess inclusion criterion #10 and exclusion criterion #18	Section 8.2.5
12. Laboratory urinalysis/microscopy		Section 8.2.3
13. Urine culture	To select adapted antibiotics for screening urodynamics and Treatment 1	Section 8.2.4 Section 6.4.1.3
14. Haematology and serum chemistry	To assess exclusion criterion #29 when results are available	Section 8.2.1 Section 8.2.2
15. Anti BTX-A antibodies	Results will not be available until after study completion	Section 8.2.6
16. Urinary tract ultrasound	Only if necessary per inclusion criterion #11	Section 5.2.2.3
17. Dispense bladder diary	Including training subject (and caregiver) on proper usage of bladder diary	Section 7.3.1 and Appendix 1

BTX-A=botulinum toxin type A; NDO=neurogenic detrusor overactivity.

5.2.1.2 *Screening Visit 2*

Electronic bladder diary data may be reviewed by the site prior to Screening Visit 2. If there has been no issue with bladder diary completion (see Section 17.6) and the subject is ineligible (inclusion criterion #13, inclusion criterion #14, and exclusion criterion #28) then the subject may be considered as a “screen failure” at that point, and does not need to attend Screening Visit 2 (arrangements should be made to return the bladder diary device to the site). See Appendix 1 for details.

The suggested order of procedures for Screening Visit 2 is shown in Table 7.

Table 7 Order of Procedures for Screening Visit 2

Suggested order of procedures	Comment	Details of procedure
1. Bladder diary review	Must confirm bladder diary eligibility (inclusion criterion #13, inclusion criterion #14, and exclusion criterion #28) prior to commencing urodynamic (filling cystometry) procedure.	Section 7.3.1 and Appendix 1
2. Concomitant medications and therapies	In particular, antibiotic prophylaxis for the urodynamic procedure should be recorded.	Section 5.2.2.2 Section 6.4
3. Concomitant treatments for NDO		Section 5.2.2.2
4. Inclusion/exclusion criteria	Including check of laboratory results to verify exclusion criterion #29.	Section 4.1 Section 4.2
5. Adverse events		Section 8.1
6. Dispense antibiotics	
 C [REDACTED] C [REDACTED] I [REDACTED] I [REDACTED] I [REDACTED] I [REDACTED] I [REDACTED] I [REDACTED] 
	Section 6.4.1.2
7. Urodynamics (filling cystometry)	
 C [REDACTED] C [REDACTED] I [REDACTED] I [REDACTED] I [REDACTED] I [REDACTED] I [REDACTED] 
	Section 7.3.2 and Study Specific Urodynamic Manual Section 5.2.3 Section 6.4.1.2 Table 18

IDC=involuntary detrusor contraction; IMP=investigational medicinal product; NDO=neurogenic detrusor overactivity.

5.2.2 Procedures for Screening and Enrolment

5.2.2.1 *Informed Consent*

Signed and dated informed consent must be obtained prior to performing any Screening procedures.

After informed consent is obtained, subjects will be allocated a subject number. All screened subjects must be identifiable throughout the study. The investigator will maintain a list of subject numbers and names to enable records to be found at a later date if required.

Patients who fail Screening cannot be re-screened for entry into this trial.

5.2.2.2 *Other Data to be Collected at Screening*

For full details of data collection refer to the eCRF completion guide. Data will be collected for the following variables:

- Demographic data
 - Date or year of birth, sex, race, and ethnicity according to local regulations
- Medical/surgical/NDO history
In particular relevant underlying neurological condition details including:
 - all subjects:
 - date of development of NDO symptoms.
 - subjects with SCI:
 - neurological level of stable SCI injury
 - date of stable SCI injury
 - cause of stable SCI (e.g. traumatic, vascular/infarction, focal mechanical compression)
 - American Spinal Injury Association (ASIA) Grade (A, B, C, D, E)
 - neurological syndrome (e.g. complete SCI, incomplete SCI, anterior cord, central cord, Brown-Sequard etc.).
 - subjects with MS:
 - date of onset of MS (initial diagnosis)
 - level of mobility (requirement for wheelchair)
 - classification (relapsing remitting, secondary progressive, primary progressive, relapsing progressive).
- Prior medications and therapies:
 - all non-NDO medications within the last 30 days
 - all previous medications taken for NDO (regardless of time period) in particular:
 - any previous BTX-A usage (including brand/trade name, dose, indication and location of injections)
 - previous usage of anticholinergic, beta-3 agonist, or any other medication for bladder/lower urinary tract symptoms
 - previous neuromodulation or electrostimulation usage (including date of insertion for implanted devices and date of switching device off)
 - previous catheterisation usage (including use of indwelling catheter and CIC).
- Concomitant medications and therapies (see [Section 6.4](#))
- Concomitant treatments for NDO (see [Section 6.4.2.1](#)).

5.2.2.3 *Urinary Tract Ultrasound at Screening*

This is only required if the subject does not have an adequate documented urinary tract ultrasound available from within 6 months prior to Screening which confirms that no medical issues exist that would preclude entry into the study (e.g. bladder stones or unexplained renal mass).

If required the ultrasound may be performed at any time during the Screening period. The results must be reviewed by the investigator prior to randomisation.

5.2.3 Treatment Visit (Day 1)

The Treatment Visit should be performed within 14 days of Screening Visit 2. However, where a UTI occurs and impacts the ability to perform IMP administration the time to the Treatment Visit can be extended until the UTI is resolved.

The suggested order of procedures for the Treatment Visit is shown in [Table 8](#).

Table 8 Order of Procedures for Treatment Visit (Day 1)

Suggested order of procedures	Comment	Details of procedure
1. I-QoL and EQ-5D-5L	This must be the first procedure performed at this visit.	Section 7.3.3 Section 7.3.3.1 Section 7.3.3.2
2. Concomitant medications and therapies	In particular, antibiotic prophylaxis for the treatment administration should be recorded.	Section 5.2.2.2 Section 6.4
3. Concomitant treatments for NDO		Section 6.4.2.1
4. Inclusion/exclusion criteria		Section 4.1 Section 4.2
5. Adverse events	Timing of adverse event (pre- or post-treatment) must be recorded.	Section 8.1
6. Vital signs	Must be performed prior to and approximately 30 minutes after treatment administration.	Section 8.4
7. Urine pregnancy test	Must be performed prior to randomisation (even if negative at Screening) in females of childbearing potential. If positive then subject must be considered a screen failure (inclusion criterion #10 and exclusion criterion #18).	Section 8.2.5
8. Randomisation	Must be performed only: 
 when all inclusion and exclusion criteria are confirmed (final eligibility); if adapted prophylactic antibiotics were commenced 3 or more days prior; if the subject does not have any symptoms suggestive of a UTI; if medications with anticoagulant effects were stopped at least 3 days earlier. Under no circumstances will subjects be randomised more than once in the study.	Section 3.3.1 Section 6.3.1 Section 6.2.1 Section 6.2.2
9. IMP administration	Subjects to be observed for at least 30 minutes following administration.	Section 6

EQ-5D-5L=EuroQol 5-dimension 5-level; IMP=investigational medicinal product; I-QoL=incontinence quality of life; NDO=neurogenic detrusor overactivity; UTI=urinary tract infection.

It is permissible to perform the Treatment Visit on the same day as Screening Visit 2:

- If adapted prophylactic antibiotics (based on the screening urine culture and sensitivity) were started 3 days prior to the combined Screening Visit 2/Treatment Visit. See [Section 6.4.1.2](#) and [Table 18](#)
- If all Screening Visit 2 procedures are performed first and the subject is assessed as being eligible for treatment.

If Screening Visit 2 and the Treatment Visit are performed on the same day then procedures that are common to both visits do not need to be performed twice.

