- b Pregnancy test to be performed only in females of childbearing potential. Must be performed prior to randomisation on the day of treatment.
- c Laboratory urinalysis/microscopy and urine culture to be performed at any follow-up visit if there is a suspicion of urinary tract infection based on subject symptoms. See [Section 6.4.1.3](#) for further details.
- d Bladder diary device to be returned when subject completes study (e.g. in the event of screen failure, EOS Visit, Early Withdrawal Visit, etc.)
- e mPGI-I will be completed on the electronic bladder diary device and should be completed at home prior to the visit.
- f Body weight and height will be measured at Screening Visit 1 only.
- g Urinary tract ultrasound is only required if no adequate documented urinary tract ultrasound is available in the 6 months prior to Screening (see inclusion criterion #11).
- h Treatment Visit should occur within 14 days of Screening Visit 2 (where a UTI occurs and impacts the ability to perform IMP administration the time to the Treatment Visit can be extended until the UTI is resolved). Both visits may be performed on the same day, as long as all Screening Visit 2 procedures are performed prior to the Treatment Visit procedures and antibiotics were commenced 3 or more days prior to treatment (see [Section 6.4.1.2](#)).
- i Adapted antibiotics based on screening urine culture sensitivities must be provided to cover both the urodynamic procedure (at least 2-day course starting on the day of the urodynamics) and to cover the treatment administration **CCCCI** See [Section 6.4.1.2](#) for further details.
- j Site should check if bladder diary has been commenced at least 8 days prior to visit. If not commenced then site should contact subject to remind subject (and/or caregiver) to commence collecting bladder diary data. Electronic bladder diary data may be reviewed by the site prior to the visit (recommended, to check if bladder diary is fully completed).
- k Screening urodynamics should only be performed if the subject is eligible based on a valid screening 7-day bladder diary.
- l At the Treatment Visit, vital signs will be recorded before and at least 30 minutes after treatment administration. In addition, blood pressure and heart rate will be monitored during the entire treatment procedure in subjects with spinal cord injury with vertebral lesions above the T6 level.

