5.2.4.3 Week 6 Clinic Visit after First Treatment

The Week 6 Visit following the first study treatment is the primary study timepoint.

The suggested order of procedures shown in [Table 11](#) is to be performed at the Week 6 Visit following the first study treatment. For activities required at the Week 6 Visit after retreatments, refer to [Section 5.2.4.4](#).

Table 11 Order of Procedures for Week 6 Clinic Visit After First Treatment

Suggested order of procedures	Comment	Details of procedure
1. I-QoL and EQ-5D-5L	This must be performed prior to any other procedures at this visit.	Section 7.3.3 Section 7.3.3.1 Section 7.3.3.2
2. mPGI-I	This should be performed electronically by the subject prior to attending the visit, otherwise subject should complete during the visit prior to undergoing any other procedures.	Section 7.3.3.3
3. Bladder diary review	May be reviewed prior to the visit. Review should occur during the visit if it has not been done beforehand.	Section 7.3.1 and Appendix 1 .
4. Concomitant medications and therapies		Section 5.2.2.2 Section 6.4
5. Concomitant treatments for NDO		Section 6.4.2.1
6. Adverse events		Section 8.1
7. Vital signs	Must be performed prior to any physical procedure at the visit.	Section 8.4
8. Physical examination (symptom based)	New clinically significant abnormalities should be reported as AEs.	Section 8.3
9. Laboratory urinalysis/ microscopy		Section 8.2.3
10. Urine culture	Must be taken before commencing prophylactic empiric antibiotics for the urodynamics (can also be used for optional adapted prophylactic antibiotic selection).	Section 6.4.1.2 Section 8.2.4 Table 18
11. Haematology and serum chemistry		Section 8.2.1 Section 8.2.2
12. Anti BTX-A antibodies	To be sampled from subject at the same time as the haematology and serum chemistry samples.	Section 8.2.6
13. Dispense antibiotics	Empiric (or optional adapted) prophylactic antibiotics prior to the urodynamic procedure.	Section 6.4.1.2
14. Urodynamics (filling cystometry)		Section 7.3.2 and Study Specific Urodynamic Manual
15. Remind subject to complete the bladder diary	Should ideally be completed in the 7 days immediately prior to the next visit. Should not be commenced any earlier than 14 days prior to the Week 12 Visit	Section 7.3.1 and Appendix 1 .

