3.2.1 Hierarchical Analysis of Selected Secondary Endpoints

A hierarchical analysis will be performed in the order listed for the following secondary efficacy endpoints at Week 6 after Treatment 1:

- 1) Mean change from study Baseline (assessed at Screening) in the MCC:
 - measured by urodynamic filling cystometry.
- 2) Mean change from study Baseline (assessed at Screening) in the MDP during storage:
 - measured by urodynamic filling cystometry.
- 3) Mean change from study Baseline (assessed at Screening) in the Vol@1stIDC:
 - measured by urodynamic filling cystometry.
- 4) Proportion of subjects with no episodes of UI (i.e. continence is achieved):
 - measured by 7-day bladder diary.
- 5) Proportion of subjects with no IDCs during storage:
 - measured by urodynamic filling cystometry.
- 6) Mean change from study Baseline (assessed at Screening) in the I-QoL total summary score:
 - measured by patient-reported questionnaire.

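### On a combined Screening Visit 2/Treatment Visit day, the visible ordering rule puts the baseline I-QoL and EQ-5D-5L after same-day cystometry, against Protocol 7.3.3 and unlike Week 6

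*Protocol*

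**What the plan says.** **Combined day.** Protocol 5.2.3 states: "It is permissible to perform the Treatment Visit on the same day as Screening Visit 2". Two conditions follow. One concerns antibiotic timing; the other is "If all Screening Visit 2 procedures are performed first and the subject is assessed as being eligible for treatment". Footnote h of Table 4, with matching words in Table 2, allows the shared day "as long as all Screening Visit 2 procedures are performed prior to the Treatment Visit procedures".

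**What belongs to which visit.** Protocol Table 7 lists filling cystometry as item 7 of Screening Visit 2 and has no I-QoL or EQ-5D-5L. Table 8 lists the two questionnaires as item 1 of the Treatment Visit, with the comment "This must be the first procedure performed at this visit". Table 4 shows no other pre-treatment administration, and Table 19 names the Treatment Visit as their study baseline.

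**Timing of questionnaires.** Protocol 7.3.3 says I-QoL and EQ-5D-5L should be completed when the site visit begins, as one of its guidelines for accurate and unbiased answers. At Week 6, Table 11 says of them "This must be performed prior to any other procedures at this visit"; cystometry is item 14 of that visit.

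**Use in the analysis.** Item 6 of the hierarchy in SAP 3.2.1 is "Mean change from study Baseline (assessed at Screening) in the I-QoL total summary score". SAP 7.6.5 analyses it with the primary MMRM, which has baseline as a covariate. SAP section 3 defines study baseline as the last value before first IMP and uses it for every treatment cycle.

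**The concern.** Section 7.3.3 exists so that these questionnaires are answered before anything is done to the subject on that attendance. A site that follows the combined-day rule as written will catheterise the subject, fill the bladder and only then hand over the baseline I-QoL and EQ-5D-5L. The same subject's Week 6 questionnaire comes before cystometry.

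The affected score is the baseline of a confirmatory secondary endpoint, and no Screening score is scheduled to replace it. Because study baseline is reused in all cycles, the same score also enters the change values after retreatment. EQ-5D-5L, which is exploratory here, is taken at the same moment and asks about pain/discomfort and anxiety/depression, which an invasive test could plausibly affect for some hours.

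**Working it through.** No arithmetic in the plan bears on this point. The check is whether any order of procedures on a combined day satisfies all the visible rules. Two orders are possible for the questionnaires.

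| Rule | Order A: Screening Visit 2 procedures, then questionnaires | Order B: questionnaires on arrival, then Screening Visit 2 procedures |
|---|---|---|
| Protocol 5.2.3 condition | met | not met |
| Footnote h, Tables 2 and 4 | met | not met |
| Table 8 comment, 'visit' read as the Treatment Visit part | met | met |
| Table 8 comment, 'visit' read as the whole attendance | not met | met |
| Protocol 7.3.3, start of the site visit | not met | met |
| Same conditions as Week 6 (Table 11) | no | yes |

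1. Order A is what the conditions in 5.2.3 and footnote h require. It fails 7.3.3 and puts the questionnaires after cystometry.
2. Order B meets 7.3.3 and matches Week 6, but a Treatment Visit procedure then precedes Screening Visit 2 procedures, against 5.2.3 and footnote h.
3. No order meets 5.2.3, footnote h and 7.3.3 together.
4. The relief in 5.2.3 from repeating procedures applies to those common to both visits. The questionnaires are not on the Screening Visit 2 list, so it does not reach them.

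The consequence can be traced in symbols only. Let *p* be the share of subjects with a combined day and *d* the mean shift in baseline I-QoL caused by same-day cystometry. The documents give neither, and *d* could be zero.

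- Mean observed baseline moves by *p* × *d*, so mean within-arm change (Week 6 minus baseline) moves by the same amount in the opposite direction.
- Baseline variance gains a component *p*(1 − *p*)*d*² if the shift is the same size in every affected subject and unrelated to the underlying score. It adds to the existing variance rather than to the SD, so the SD grows by less than the square root of this component.
- The combined day precedes allocation, so *p* and *d* are equal across arms in expectation. Baseline is a linear covariate in the MMRM, so subtracting it from the response alters its own coefficient and not the treatment contrast. What remains for the contrast is a slightly less informative covariate.

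**The case against.** **There is no literal contradiction with Table 8.** A reader might infer that 5.2.3 and the Table 8 comment cannot both be obeyed. That is not established. If 'visit' there means the Treatment Visit part, a site can finish Screening Visit 2 and open the Treatment Visit with I-QoL. This stands, and it is why the conflict lies between 5.2.3 with footnote h and section 7.3.3. The milder reading does not remove the consequence: on it, I-QoL follows cystometry.

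**Section 7.3.3 is worded as a guideline.** True: it says 'should', whereas 5.2.3 sets a condition for combining the visits. A site weighing the two would more likely follow the condition, which makes the unwanted order the likelier one.

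**The governing text may be redacted.** Table 18 is titled as covering antibiotic prophylaxis and combining visits, 5.2.3 refers to it, and it is blacked out, as is much of 6.4.1.2. It may address the order. If it does, 5.2.3 and footnote h still say otherwise without exception and need aligning.

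**Subjects with separate visits have also had cystometry.** This stands. They had it at Screening Visit 2, normally within the previous 14 days. The difference is same-day versus earlier-day cystometry. Nor do the documents say when subjects are told they are eligible, so knowledge of eligibility cannot be claimed to separate the two groups.

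**The baseline label is already resolved elsewhere.** A reader might take the Screening label in SAP 3.2.1 and Protocol 3.2.2.2 to mean that the baseline is missing or ambiguous. It is not: Table 19 and SAP section 3 settle which value is used, only one pre-treatment I-QoL is scheduled, and SAP 7.6.5 restates item 6 without the label. It is a wording slip.

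**Conclusion.** The point holds as an ordering conflict between Protocol 5.2.3 with footnote h and Protocol 7.3.3. Following the combined-day rule puts the only scheduled pre-treatment I-QoL and EQ-5D-5L after same-day cystometry, while Week 6 is always before it. The result is inconsistent baseline conditions in an unknown share of subjects for the last of six hierarchical endpoints and for EQ-5D-5L.

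A reader might infer bias between arms or a threat to the type I error rate. The documents do not support either: the questionnaires are completed before randomisation, any shift is balanced across arms in expectation, and the tested quantity is the between-arm difference. The effect falls on within-arm change from baseline, on comparability across sites that combine visits to different degrees, and modestly on precision. Sample size is unaffected. No numerical size can be given, because the frequency of combined days and the effect of cystometry on the score would both have to be invented.

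The conclusion rests on the visible text and on the assumption that some sites use the combined day.

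**What to change.** In Protocol 5.2.3 and in footnote h of Tables 2 and 4, exempt the questionnaires from the Screening Visit 2-first condition. Suggested wording: *On a combined day, I-QoL and EQ-5D-5L are completed on arrival, before urodynamics. The other Screening Visit 2 procedures are then completed before the other Treatment Visit procedures.* Repeat this in the comments of Tables 7 and 8, and check Table 18 for agreement.

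As a minor alignment, in Protocol 3.2.2.2 and SAP 3.2.1, item 6, replace the reference to Screening with the Treatment Visit before IMP administration, to match Table 19 and SAP section 3.

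The cost is an amendment of wording and a site instruction. The one practical downside is that a subject who then fails eligibility on that day will have completed two questionnaires to no purpose. Eligibility criteria, antibiotic rules, treatment and the analysis model are unchanged.

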5.2.4 Follow-up Period (after First Treatment and Retreatments)

Routine Follow-up Visits after the first treatment and after retreatments are almost identical, therefore visit details in this section refers to follow-up for both the first treatment and retreatments (any differences in follow-up will be highlighted).

